12.2.2 Serious Adverse Event (SAE)

An AE or SAR is considered "serious" if, in the view of either the investigator or the Sponsor, it results in any of the following outcomes: Death, a life-threatening AE, inpatient hospitalization or prolongation of existing hospitalization, a persistent or significant incapacity or substantial disruption of the ability to conduct normal life functions, or a congenital anomaly/birth defect. Important medical events that may not result in death, be life-threatening, or require hospitalization may be considered serious when, based upon appropriate medical judgment, they may jeopardize the

patient or subject and may require medical or surgical intervention to prevent one of the outcomes listed in this definition. Examples of such medical events include allergic bronchospasm requiring intensive treatment in an emergency room or at home, blood dyscrasias or convulsions that do not result in inpatient hospitalization, or the development of drug dependency or drug abuse (21 CFR 312.32(a)).

Elective hospitalizations are not to be reported as an SAE unless hospitalization is prolonged due to complications.

12.3 Grading and Attribution of Adverse Events

12.3.1 Grading Criteria

The study site will grade the severity of AEs experienced by the study participants according to the criteria set forth in the [NCI-CTCAE Version 5.0](#). This document (referred to herein as the NCI-CTCAE manual) provides a common language to describe levels of severity, to analyze and interpret data, and to articulate the clinical significance of all AEs. The NCI-CTCAE has been reviewed by the study investigators and sponsor and has been deemed appropriate for the participant population to be studied in this protocol.

AEs will be graded on a scale from 1 to 5 according to the following standards in the NCI-CTCAE manual:

Grade 1 = Mild; asymptomatic or mild symptoms; clinical or diagnostic observations only; intervention not indicated.

Grade 2 = Moderate; minimal, local, or noninvasive intervention indicated; limiting age-appropriate instrumental activities of daily life (e.g., preparing meals, shopping for groceries or clothes, using the telephone, managing money, etc.).

Grade 3 = Severe or medically significant but not immediately life-threatening = Hospitalization or prolongation of hospitalization indicated; disabling; limiting self-care activities of daily life (e.g., bathing, dressing, feeding self, taking medications, etc.).

Grade 4 = Life-threatening consequences; urgent intervention indicated.

Grade 5 = Death.

Events grade 1 or higher will be recorded on the appropriate AE electronic case report form (eCRF) for this study.

For grading an abnormal value or result of a clinical or laboratory evaluation (including, but not limited to, a radiograph, an ultrasound, an electrocardiogram etc.), an AE is defined as an increase in grade from baseline or from the last post-baseline value that doesn't meet grading criteria. Changes in grade from screening to baseline will also be recorded as AEs. If a specific event or result from a given clinical or laboratory evaluation is not included in the NCI-CTCAE manual, then an abnormal result would be considered an AE if changes in therapy or monitoring are implemented as a result of the event/result.

For additional information and a printable version of the NCI-CTCAE manual, consult the NCI-CTCAE web site: <http://ctep.cancer.gov/reporting/ctc.html>.

12.3.2 Attribution Definitions

The relationship, or attribution, of an AE to the study therapy regimen or study procedure(s) will initially be determined by the site investigator and recorded on the appropriate AE eCRF. Final determination of attribution for safety reporting will be determined by DAIT/NIAID Medical Monitor. The relationship of an AE to study

therapy regimen or procedures will be determined using the descriptors and definitions provided in Table 12.3.2.

Table 12.3.2 Attribution of Adverse Events

Code	Descriptor	Relationship (to study treatment medications and/or other study procedure)
UNRELATED CATEGORY		
1	Not Related	The AE is clearly not related: there is insufficient evidence to suggest a causal relationship.
RELATED CATEGORIES		
2	Possibly Related	The AE has a reasonable possibility to be related; there is evidence to suggest a causal relationship.
3	Related	The AE is clearly related.

12.4 Collection and Recording of Adverse Events

12.4.1 Collection Period

AEs will be collected from the time of consent, until a participant completes study participation, or until 30 days after their last study treatment dose if he/she prematurely withdraws (without withdrawing consent) or is withdrawn from the study. Prior to study treatment, AEs will be collected according to the study mandated procedures he/she last completed, as applicable. AE collection periods for study mandated procedures are described in [Section 12.2.1](#).

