8.9 End of Study Assessment

The following procedures and assessments will be conducted at the End of Study Assessment:

- Interim medical history
- Physical examination (abbreviated at investigator discretion)
- Assessments of AD severity (EASI, IGA, SCORAD, NESS, PP-NRS, TAA, and targeted EASI) for DNAD and LTD participants only
- Allergic disease questionnaires
- Confirm pregnancy status (if applicable)
 - At investigator discretion and subject to each individual clinical institution's policies, individuals may be asked to complete a urine pregnancy test.
- Assessment of concomitant medications
- Vital signs, including temperature, blood pressure, heart rate, and respiratory rate
- Blood collection; approximately 20 mL for serum/plasma biomarkers and approximately 2 mL for a CBC with differential
- Photographs will be taken of the measured lesional and non-lesional sites for collection of skin swabs, tape strips, and biopsies, as applicable
- Skin swab collection; up to 9 swabs
- STS collection; up to 60 STS
- Up to three optional 2.5 mm skin biopsies for molecular assays, adults only
- Assessment of AEs

At the conclusion of this visit, participants will be allowed to resume use of prohibited medications/procedures as described in [Section 7.3](#). Participants will be allowed to receive live (attenuated) vaccinations, as needed. They will be allowed to resume bathing/showering, use of chlorinated pools and hot tubs, sunscreen, and moisturizers without restrictions.

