8.11 Early Withdrawal/Termination Follow-Up Phone Call

A final telephone visit will occur for participants who prematurely withdraw or are withdrawn, any time after Day 7. The timing of this visit will vary per participant, based on received study treatments and/or completed study procedures. This visit will occur 30 days after the last dose of treatment *and* after the longest AE observation period for any completed study procedures. The visit will be brief, and participants will be asked to report any new AEs, answer questions regarding the status of their AD, as applicable, and report on any new concomitant medication use. Individuals who can become pregnant, as defined in the study manual of procedures, will be asked whether they have tested positive to a pregnancy test since their last visit.

AEs discovered and/or reviewed during this phone call will be followed as described in [Section 12.4.3](#). For many participants who prematurely withdraw or are withdrawn, this final phone call will coincide with the conclusion of all non-serious AE surveillance. However, any participant with an ongoing SAE will be followed until it resolves with or without sequelae, or the SAE stabilizes, or until the participant withdraws consent, whichever occurs first. Monitoring of a pregnant participant shall continue until the conclusion of the pregnancy.

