11.1 Participant Completion

Participation will be considered complete for each participant at the conclusion of the End of Study Assessment (Day 168-224). Participants that complete an Early Termination Visit will not be considered as having completed the study.

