12.2 Definitions

12.2.1 Adverse Event (AE)

An AE is any untoward or unfavorable medical occurrence associated with the subject's participation in the research, whether or not considered related to the subject's participation in the research (modified from the definition of AEs in 21 CFR 312.32(a), the International Council for Harmonisation of Technical Requirements for Pharmaceuticals for Human Use (ICH) E-6(R2) Guidelines for Good Clinical Practice (GCP) and OHRP "Guidance on Reviewing and Reporting Unanticipated Problems Involving Risks to Subjects or Others and Adverse Events (1/15/07)" <http://www.hhs.gov/ohrp/policy/advevntguid.html#Q2>).

The investigator must report AEs regardless of relationship to study therapy regimen or study mandated procedures.

For this study, a related AE will include any untoward or unfavorable medical occurrence associated with:

- **Study therapy regimen:**

- Vanicaream™ Moisturizing Cream, triamcinolone, hydrocortisone, and dupilumab: An AE occurring after treatment initiation

Vanicaream™ Moisturizing Cream will be the only study therapy for the non-AD and long-term dupilumab participants. Medications not provided as part of the study, even if the same as study medications, will not be considered as study treatment.

- **Study mandated procedures:**

- Blood Draw: The following events related to the blood draw procedure will be considered AEs if they occur within 48 hours of the blood draw:
 - Fainting / Vasovagal Events
 - Bruising at the puncture site larger than 2 cm in diameter

- Bleeding from the puncture site lasting more than 30 minutes
 - Swelling at the puncture site larger than 2 cm
 - Allergic reaction to topical anesthetic that requires use of rescue medications, detailed in [Section 7.4](#)
- **STS:** The following events related to the STS collection procedure will be considered AEs if they occur within 48 hours of the tape stripping:
 - Fainting / Vasovagal Events
 - Bruising at the tape stripping site larger than 2 cm in diameter
 - Bleeding from the tape stripping site lasting more than 30 minutes
 - Redness or swelling at the tape stripping site larger than 3 cm
 - Fever (> 100.4°F) x two readings separated by more than 10 hours
 - Allergic reaction to STS that requires use of rescue medications, detailed in [Section 7.4](#)

Purulent drainage from a tape stripping site within 2 weeks of the procedure will also be considered an AE.

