- **Skin Biopsy:** The following events related to the skin biopsies will be considered AEs if they occur within 48 hours of the skin biopsies:
 - Fainting / Vasovagal Events
 - Bleeding at skin biopsy site lasting more than 6 hours
 - Redness or swelling at biopsy site larger than 2 cm in diameter
 - Fever (> 100.4°F) x two readings separated by more than 10 hours
 - Allergic reaction to lidocaine that requires use of rescue medications, detailed in [Section 7.4](#)

Purulent drainage from a skin biopsy site within 2 weeks of the procedure will also be considered an AE.

Suspected Adverse Reaction (SAR)

Any AE for which there is a reasonable possibility that the study drug caused the AE. For the purposes of safety reporting, 'reasonable possibility' means there is evidence to suggest a causal relationship between the drug and the AE. An SAR implies a lesser degree of certainty about causality than AR, which means any AE caused by a drug (21 CFR 312.32(a)).

Unexpected Adverse Event

An AE or SAR is considered "unexpected" if it is not listed in the package insert or is not listed at the specificity, severity, or rate of occurrence that has been observed.

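### For participants who complete the study, AE collection closes with the End of Study visit, so the 48-hour and 2-week windows for that visit's own procedures have no scheduled follow-up

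*Protocol*

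**What the plan says.** Protocol Section 12.4.1 sets the collection period: "AEs will be collected from the time of consent, until a participant completes study participation". For those who leave early without withdrawing consent it sets a different end, 30 days after the last study treatment dose. Section 11.1 fixes the completer's end point: "Participation will be considered complete for each participant at the conclusion of the End of Study Assessment (Day 168-224". Section 12.4.3 also ends follow-up of an already recorded non-serious AE at the end of participation, if it has not resolved or stabilized sooner.

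Section 8.9 lists the procedures at that closing visit:
- "Blood collection; approximately 20 mL for serum/plasma biomarkers and approximately 2 mL for a CBC with differential"
- "STS collection; up to 60 STS"
- "Up to three optional 2.5 mm skin biopsies for molecular assays, adults only"

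Section 12.2.1 attaches time windows to the same procedures. For blood, "The following events related to the blood draw procedure will be considered AEs if they occur within 48 hours of the blood draw"; tape stripping and biopsy have the same 48-hour rule. For biopsy it adds: "Purulent drainage from a skin biopsy site within 2 weeks of the procedure will also be considered an AE". A matching 2-week sentence covers tape stripping.

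The only contact planned after a participant's last visit is in Section 8.11: "A final telephone visit will occur for participants who prematurely withdraw or are withdrawn, any time after Day 7". That call must fall both 30 days after the last treatment dose and after the longest AE window for any procedure done. Section 11.4 and the Appendix A footnotes limit it to the same people.

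**The concern.** The protocol has decided how long after each procedure certain events count as AEs. For completers, it stops looking before those periods have run for the final session.

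The events most exposed are those that take time to appear. Purulent drainage is the clearest case, because it is the reason for the 2-week window. Prolonged bleeding, spreading redness or swelling, and fever confirmed by a second reading more than 10 hours later can also arise after the participant has gone home.

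The comparison with early leavers sharpens the point. The Early Termination Visit (Section 8.10) has the same sampling limits as End of Study: up to 60 tape strips and up to three optional biopsies. A participant sampled there is called after the longest window has closed. A completer with identical samples is not, and the protocol gives no reason for the difference.

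Section 8.9 also omits the paragraph, present in Sections 8.2 to 8.8 and 8.12, that tells participants when to contact the clinic about AEs.

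At stake are complete procedure-related AE listings for the Data Safety Monitoring Board, and the participant's route to being followed for an event the protocol itself defines.

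**Working it through.** The plan gives no figure to reproduce. The check is a timeline.

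**Inputs.** Visit days and windows come from Section 8.13 and Appendix A, the end of collection from Sections 12.4.1 and 11.1, and the event windows (2 days and 14 days) from Section 12.2.1.

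**Formula.** Days observed after a procedure = day AE collection ends − day of procedure.

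| Group | Scheduled tape-strip days | Days observed afterwards |
|---|---|---|
| Non-AD | 0, 7, 35, 91, 140, 168 | 168, 161, 133, 77, 28, 0 |
| Topical steroid responders | 0, 7, 35, 91, 140, 168 | 168, 161, 133, 77, 28, 0 |
| Non-responders starting dupilumab at Day 35 | 0, 7, 35, 63, 140, 168 | 168, 161, 133, 105, 28, 0 |
| Long-term dupilumab | 0, 7, 63, 140, 168 | 168, 161, 105, 28, 0 |

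**Shortest gap before the last visit.** With the penultimate visit as late as allowed and End of Study as early as allowed, the gap is 165 − 143 = 22 days. For non-responders, counted from dupilumab initiation, it is 130 − 108 = 22 days, whenever they started. Both exceed 14, so every window after an earlier session is covered in full.

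**Last session.** The required time is 2 days for the 48-hour events and 14 days for purulent drainage. The time given is 0 days once the visit closes.

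**Share of sampling occasions affected.**
- Tape strips: 1 of 6 for non-AD participants, steroid responders and non-responders who start dupilumab at Day 35; 1 of 5 for long-term dupilumab participants.
- Scheduled biopsy occasions (adults): 1 of 2 for non-AD participants and steroid responders (Day 7, End of Study); 1 of 3 for long-term dupilumab participants (Day 7, Day 140, End of Study); 1 of 4 for non-responders (Day 7, dupilumab initiation, 15 Week, End of Study).

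**Scale.** Section 13.7.1 plans 600 participants, and Section 13.4.1 divides them into 400 adults and 200 children. Under the 20% dropout used as a power scenario, completers number 600 × 0.8 = 480, of whom 400 × 0.8 = 320 are adults. With no dropout the figures are 600 and 400. Every group is scheduled for blood and tape strips at End of Study. Biopsy is optional and for adults only, and uptake is not stated.

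**Is dupilumab follow-up also short?** The last scheduled every-two-week dose falls on Day 133 when dupilumab starts at Day 35, and 168 − 133 = 35 days, which exceeds the 30 days used for early leavers. The gap therefore concerns the procedures, not follow-up after dupilumab.

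**The case against.** The strongest reply is the closing sentence of Section 12.4.1, which refers to the Section 12.2.1 windows as AE collection periods. Read alone, it could carry collection past End of Study. It follows a sentence confined to the time before study treatment, however, and it provides no contact with a completer. It makes the text ambiguous without closing the gap.

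Several further points stand and limit the concern:
- A reader might infer that procedure windows are unobserved throughout the study. They are not: only the last session is affected.
- A reader might infer that nothing at all is seen after the last procedures. Section 8.9 includes an AE assessment, and some listed events, such as fainting or a reaction to lidocaine within minutes, can occur and be recorded during the visit.
- A reader might infer that later events can never be recorded or counted toward the Section 11.5 stopping rule. The documents do not say so. Section 12.4.2 accepts unsolicited calls, and contact details are given at repeated earlier visits. Appendix A tells non-AD and long-term dupilumab participants to report symptoms at sampling sites. Section 12.5.1 requires SAE reports within 24 hours of discovery with no stated end date, SAE follow-up under 12.4.3 is not tied to completion, and 11.5 sets no cut-off at completion.
- Sections 5.3.6 and 5.3.7 describe tape-strip infection as extremely low risk, biopsy-site infection as unusual and significant bleeding as rare.
- The manual of procedures, which is not available here, may add post-biopsy instructions.

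These routes depend on the participant calling or on the event being serious. They do not replace an end date that matches the protocol's own windows.

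**Conclusion.** The inconsistency is real but narrow. For completers, Sections 11.1, 12.4.1 and 12.4.3 end routine AE collection and non-serious AE follow-up when the End of Study visit closes. Section 12.2.1 defines AEs for up to 2 more days, and up to 14 for purulent drainage, after procedures done at that visit. Non-serious procedure events after the last session are likely to be under-captured; SAEs and spontaneous reports may still arrive.

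The size is about 480 completers under the 20% scenario (600 with no dropout). These are people without scheduled follow-up, not missed events, because the documents give no event rates. The 320 adults should not be read as a number biopsied.

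No primary or secondary estimand is affected. SAP Section 10 plans no safety analysis beyond the reporting described in the protocol. This should be fixed, but it does not undermine the trial's main results. The conclusion assumes that the manual of procedures does not already provide the missing follow-up.

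**What to change.** - In Sections 11.1, 12.4.1 and 12.4.3, state that for completers AE collection and follow-up run to the end of the longest Section 12.2.1 window for any procedure done at End of Study. Reword the last sentence of 12.4.1 so that it clearly applies after treatment has started as well as before.
- Add to Section 8.9 the AE-contact paragraph used at the preceding visits.
- Extend the existing Section 8.11 call to completers at about 2 weeks after End of Study, at minimum to those biopsied there, and show it in Section 8.13 and Appendix A.

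The cost is a protocol wording change, one short call per participant contacted, using a procedure already in place for early leavers, and closure of each participant's record about 2 weeks later. No new assessment or sample is needed.

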12.4.2 Collecting Adverse Events

AEs (including SAEs) may be discovered through any of these methods:

- Observing the participant
- Interviewing the participant in an objective manner [e.g., using structured questioning]
- Receiving an unsolicited complaint from the participant
- Receiving a call from the participant outside of their regular study visits; instructions for contacting the clinic will be provided to the participant
- In addition, an abnormal value or result from a clinical or laboratory evaluation can also indicate an AE, as defined in [Section 12.3](#).

12.4.3 Recording Adverse Events

Throughout the study, the investigator will record AEs and SAEs as described previously ([Section 12.2](#)) on the appropriate AE/SAE eCRF regardless of the relationship to study therapy regimen or study procedure.

Once recorded, an AE will be followed until it resolves with or without sequelae, or the AE stabilizes, or until the end of study participation, or until 30 days after the participant prematurely withdraws without withdrawing consent, or until 30 days after the participant is prematurely withdrawn from the study, whichever occurs first.

Once recorded, an SAE will be followed until it resolves with or without sequelae, or the SAE stabilizes, or until the participant withdraws consent, whichever occurs first.

Monitoring of a pregnant participant shall continue until the conclusion of the pregnancy.

12.5 Reporting of Serious Adverse Events and Adverse Events

12.5.1 Reporting of Serious Adverse Events to DAIT/NIAID

This section describes the responsibilities of the site investigator to report SAEs to the DAIT/NIAID and the Statistical and Clinical Coordinating Center (SACCC) via the SAE eCRF. Timely reporting of AEs is required by 21 CFR and ICH E6 guidelines.

Site investigators will report all SAEs (see [Section 12.2.2](#)), regardless of relationship or expectedness within 24 hours of discovering the event.

For SAEs, all requested information on the AE/SAE eCRF will be provided. However, unavailable details of the event will not delay submission of the known information. Initial SAE eCRFs should include as much information as possible, but at a minimum must include the following:

- AE term
- Relationship to study therapy regimen and procedures
- Reason why the event is serious
- Supplementary CRF pages that are current at the time of SAE reporting: medical history, concomitant medications, demographics, study treatment administration

As additional details become available, the AE/SAE eCRF will be updated and submitted. Every time the SAE eCRF is submitted, it should be electronically signed by the investigator or sub-investigator.

For additional information regarding SAE reporting, contact Rho Product Safety:

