11.5 Study Stopping Rules

Study enrollment will be suspended pending Division of Allergy, Immunology, and Transplantation (DAIT)/NIAID and NIAID Allergy and Asthma Data Safety Monitoring Board (DSMB) expedited review of all pertinent data if any of the following occur:

- 1 death, or life-threatening AE, that is at least possibly related to the study therapy regimen or procedures
- A grade 3 or higher AE that is at least possibly related to the study therapy regimen or procedures in two or more participants

The study may not be resumed until all pertinent information is reviewed by DAIT/NIAID, NIAID Allergy and Asthma DSMB, and the central Institutional Review Board (IRB), and all parties concur with the resumption of the study. Local IRBs will be informed of the study suspension and the NIAID/DSMB/Central IRB decision on resumption of the study.

The study may be suspended or terminated by DAIT/NIAID upon review of any observations, events, or new information that merits such action.

12 Safety Monitoring and Reporting

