12.8 Review of Safety Information

12.8.1 Medical Monitor Review

The DAIT/NIAID Medical Monitor shall receive monthly reports from the SACCC compiling new and accumulating information on AEs, SAEs, and pregnancies recorded by the study site(s) on appropriate eCRFs.

In addition, the DAIT/NIAID Medical Monitor shall review and make decisions on the disposition of the SAE and pregnancy reports received by the SACCC (See Sections [12.5.1](#) and [12.6](#)).

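### The second stopping rule counts related grade 3 AEs whether or not serious, but only SAEs have a dated reporting route, so a trigger that turns on a non-serious event can go unnoticed for up to about a month

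*Protocol*

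**What the plan says.** Protocol 11.5 has two triggers. The first is "1 death, or life-threatening AE, that is at least possibly related to the study therapy regimen or procedures". The second is "A grade 3 or higher AE that is at least possibly related to the study therapy regimen or procedures in two or more participants"; it asks for grade and relatedness, not seriousness. When either is met, "Study enrollment will be suspended pending Division of Allergy, Immunology, and Transplantation (DAIT)/NIAID" and DSMB expedited review.

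Protocol 12.3.1 grades by severity. Its description of grade 3 covers events for which hospitalisation is indicated and disabling events, and also events "limiting self-care activities of daily life". Protocol 12.2.2 defines seriousness by outcome, with a further category of important medical events that rests on judgement.

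On reporting, Protocol 12.5.1 requires sites to send all SAEs "regardless of relationship or expectedness within 24 hours of discovering the event". Protocol 12.6 gives pregnancies a 24-hour rule too. Other AEs are recorded on the eCRF (12.4.3), with no stated time limit. Protocol 12.8.1 then says: "The DAIT/NIAID Medical Monitor shall receive monthly reports from the SACCC compiling new and accumulating information on AEs, SAEs, and pregnancies". SAP section 10 describes the same monthly cycle. In 12.8.1 the monitor's decisions on individual reports are described for SAEs and pregnancies only.

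On deciding, Protocol 12.3.2 leaves the first call on relatedness to the site but adds: "Final determination of attribution for safety reporting will be determined by DAIT/NIAID Medical Monitor". Under 12.8.4 the same monitor notifies the DSMB within 24-48 hours.

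**The concern.** The rule and the reporting route use different filters. The rule selects on grade and relatedness; the fast route selects on seriousness. An event that is grade 3, related and not serious counts towards suspension, yet a site that follows the written routes has no dated duty to tell the sponsor about it.

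The count is also study-wide. In a multicenter study the two participants may be at different sites, and neither site need know of the other's case. The coordinating centre holds the data, but no section tells it to keep the tally.

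At stake is the suspension and expedited review that 11.5 promises. If detection waits for a monthly compilation, people keep enrolling after the rule has been met and the DSMB starts its review late.

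**Working it through.** **1. Which triggers are affected.** Setting 11.5 against 12.2.2, 12.5.1 and 12.8.1:

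| Trigger | Route to the medical monitor | Dated? |
|---|---|---|
| Related death or life-threatening AE | SAE report | Yes, 24 hours |
| Two related grade 3 events, both serious | SAE reports | Yes, 24 hours |
| Non-serious event first and already reported, serious event second | SAE report for the second | Yes, if someone holds the count |
| Count completed by a non-serious event, or dependent on one not yet reported | eCRF, then monthly report | No entry deadline; monthly cycle |

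The gap is the last row, plus the missing owner of the count in the third.

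**2. Where the 24-48 hours starts.** In 12.8.4 that interval covers notification of the DSMB by the monitor. It says nothing about how quickly the site informs the monitor, so it cannot shorten the earlier step.

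**3. Size of the lag in enrolments.** The documents state no figure to reproduce. Inputs from the Protocol synopsis: about 600 participants, about 390 of them DNAD, enrolled over about 29 months.

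- All participants: 600/29 = 20.7 per month.
- DNAD: 390/29 = 13.4 per month.

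I assume even accrual, a 30.4-day month, and a trigger equally likely on any day of the reporting cycle, so that the mean wait is about 15 days. Enrolments during the lag = monthly rate × lag in days / 30.4.

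| Lag | All | DNAD |
|---|---|---|
| 1 day | 20.7 × 1/30.4 = 0.7 | 0.4 |
| 2 days | 1.4 | 0.9 |
| 15 days (mean wait) | 10.2 | 6.6 |
| 30.4 days (full cycle) | 20.7 | 13.4 |

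eCRF entry time would add to the last two rows; no deadline is given, so I have not put a number on it.

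**4. Is the second trigger plausible?** The documents give no rate of related grade 3 events, so the per-participant rate p is an assumption. The chance of two or more affected participants among n is 1 − (1 − p)^n − n p (1 − p)^(n−1). Protocol 13.7.1 expects 85 + 43 = 128 participants to start dupilumab in the study.

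| Assumed p | n = 128 | n = 600 |
|---|---|---|
| 0.25% | 4% | 44% |
| 0.5% | 14% | 80% |
| 1% | 37% | 98% |
| 2% | 73% | >99% |

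Worked case, p = 1%, n = 128: 1 − 0.276 − 0.357 = 0.367. These chances include serious events. The documents give no split, so they show that the second rule could plausibly be met, not how often a non-serious event would decide it.

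**The case against.** The strongest objection is that little of grade 3 falls outside the 24-hour route. The SAE definition in 12.2.2 covers hospitalisation, incapacity that is significant even if not persistent, major interference with ordinary functioning, and important medical events in the view of investigator or sponsor. An event that stops someone bathing, dressing or feeding themselves may well qualify. This stands: a reader might infer that a grade 3 event limiting self-care is non-serious by definition, and the documents do not support that. What remains is a residue of unknown size, such as brief events or abnormal laboratory values. Classification under 12.2.2 is partly discretionary, whereas the count in 11.5 is not.

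A reader might also infer that the rule can act only when the monthly report is read. That goes too far. Protocol 12.5.1 and 12.5.3 call for timely AE reporting, the protocol chair can ask for an ad hoc DSMB review, and eCRF data sit in a central database. Someone could notice sooner. But the timeliness wording carries no deadline, 12.5.3 concerns IRBs, and the real-time checks in Protocol section 15 are for data errors. None obliges anyone to detect the trigger.

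A third tempting step is to count dupilumab starts during the lag as avoidable. Protocol 12.8.4 stops new consents but keeps participants already on therapy on treatment, and no section clearly halts their crossover to dupilumab. Nor can dupilumab begin before the 4 Week Steroid Assessment, whose window opens on Day 32, so nobody enrolled during a one-month lag would start it within that lag.

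Finally, the documents do not say which kinds of reaction the rule is meant to catch. The manual of procedures, which was not available, may contain a faster route, but 11.5, 12.5.1 and 12.8 do not refer to it for this.

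**Conclusion.** The concern holds for one class of trigger: a count under the second rule that turns on a related grade 3 event that is not an SAE. Deaths, life-threatening events and serious grade 3 events are already covered. For the affected class, suspension and expedited DSMB review can lag by up to about a month, or longer if eCRF entry is slow.

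At average accrual that is about 10 further enrolments on average and about 21 at most. About 7 and 13 of them are DNAD. The rest are NAD and LTD participants, whose only study therapy is moisturiser (Protocol 12.2.1) but who do undergo study procedures.

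These figures rest on even accrual, a trigger falling at random within the monthly cycle, and no earlier informal detection. Continued enrolment during the lag is inferred from the lack of any required earlier step; the documents do not state it. This is a cheap improvement to safety monitoring. It does not show that the monitoring fails in general.

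**What to change.** - **Protocol 12.5.1:** require any AE of grade 3 or higher that the site judges at least possibly related to study therapy or procedures to be reported within 24 hours, whether or not serious.
- **Protocol 12.8.1:** have the statistical and clinical coordinating center keep a running cross-site count against 11.5, using the site's provisional attribution until the medical monitor decides.
- **Protocol 12.8.4:** state the moment from which the 24-48 hour DSMB notification runs.

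With a 24-hour report, expected enrolments before the monitor knows fall to about 0.7, or 1.4 at 48 hours. The cost is a sentence in each place, an EDC alert on grade and relationship, and a small number of extra expedited reports. The stopping thresholds, treatment, eligibility and endpoints stay as they are.
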